We intend to perform a non-inferiority two-arm randomized controlled trial to evaluate the safety and feasibility of prophylactic salpingectomy at the time of a cesarean delivery as an initiative to avoid a missed opportunity in the primary prevention of ovarian cancer. Once enrolled and consented, women will be randomized using a stratified block randomization algorithm according to number of prior cesarean deliveries and BMI to either salpingectomy or bilateral tubal ligation. The data collection will include preoperative CBC, time of procedure, postoperative CBC at 24 hours, standard patient demographics, procedural complications, estimated blood loss, return to the OR, length of stay, pain scores and postoperative complications including readmission within 6 weeks.

Interventions and Duration

In the control arm, subjects will have sterilization performed via the Parkland or Pomeroy method of bilateral tubal ligation based on provider preference. In the study arm, a salpingectomy will be performed using a combination of suture ligation and cautery. The enrollment period will occur over two years and follow up will extend 6 weeks from surgery.

Sample Size and Population

The study population will included pregnant woman greater than 21 years old that have an indication for cesarean delivery and proper consent for permanent sterilization. The stratified block randomization will be according to number of prior cesarean deliveries (primary versus repeat cesarean delivery). The primary outcome is mean drop in hemoglobin. Assuming that a difference of 0.5 in the drop in hemoglobin between study arms would be considered as equivalent and assuming a common standard deviation of 1.1, the study will have 80% power to test for non-inferiority with 60 patients in each arm (120 totals). This calculation is based on a two-group 0.05 1-sided t-test of equivalent in means.

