5.2 Handling of Study Interventions

There are no drugs or lifestyle/behavioral interventions in the study.

The intervention being investigated is the safety of salpingectomy as a form of sterilization vs BTL at the time of Cesarean delivery. Patients meeting enrollment criteria are those who desire permanent sterilization, are correctly consented, and are planning a repeat cesarean delivery. They will be blinded to the operative intervention at the time of

enrollment and randomization; after the surgery, it will be disclosed to them the procedure they had performed.

To investigate differences in mean hemoglobin, preoperative hemoglobin and postoperative hemoglobin will be obtained for all study participants.

To investigate the differences in operative time for the different surgical procedures being studied, all surgeries will be timed beginning at the initiation of the sterilization procedure being performed (i.e., once the cesarean delivery has been completed, and just prior to starting either the tubal ligation or salpingectomy procedure).

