9.2 Sample Size and Randomization

The primary outcome is mean drop in hemoglobin. Previous studies have reported a

mean (SD) drop in hemoglobin of 1.32 (0.94) g/dl following a repeat cesarean delivery and 1.40 (1.2) following a first cesarean delivery (7). Based on our experience in 2015, we anticipate that over 75% of our cases will be repeat cesarean deliveries. Assuming that a difference of 0.5 in the drop in hemoglobin between study arms would be considered as equivalent and assuming a common standard deviation of 1.1, the study will have 80% power to test for non-inferiority with 60 patients in each arm (120 total). This calculation is based on a two-group 0.05 1-sided t-test of equivalent in means.

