9.2.1 Treatment Assignment Procedures

Once enrolled and consented, women will be randomized using a stratified block randomization algorithm prepared by the study statistician to either standard BTL or salpingectomy stratified according to number of prior cesarean deliveries (first versus repeat), and BMI (BMI < 35, BMI > 35).

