9.3 Interim analyses and Stopping Rules

No interim analysis is planned.

The study will be stopped or placed on clinical hold if the number of adverse events exceeds the thresholds detailed in section 8.

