9.4 Outcomes

9.4.1 Primary outcome

The primary outcome is mean change in preoperative to postoperative hemoglobin. These values will be collected from the patient's chart. The preoperative hemoglobin will be performed on the day of surgery. The postoperative hemoglobin will be performed the morning after surgery at least 24 hours but no greater than 48 hours after the procedure.

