9.5 Data Analyses

A 1-sided 95% confidence interval will be constructed for the difference between study arms in the mean drop in hemoglobin. In addition, the reduction in hemoglobin will be analyzed using a one-sided T-test using a change of .5g/dL. Secondary endpoints will be analyzed using two-sided T-test testing for a difference between the two study arms or a Chi-square test as appropriate. Statistical significance will be determined using a p-value of 0.05.

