12 ETHICAL CONSIDERATIONS

This study is to be conducted according to United States government regulations and Institutional research policies and procedures.

This protocol and any amendments will be submitted to a properly constituted local Institutional Review Board (IRB), in agreement with local legal prescriptions, for formal approval of the study. The decision of the IRB concerning the conduct of the study will be made in writing to the sponsor-investigator before commencement of this study.

All subjects for this study will be provided a consent form describing this study and providing sufficient information for subjects to make an informed decision about their participation in this study. This consent form will be submitted with the protocol for review and approval by the IRB for the study. The formal consent of a subject, using the Approved IRB consent form, must be obtained before that subject undergoes any study procedure. The consent form must be signed by the subject or the subject's legally authorized representative, and the individual obtaining the informed consent.

This study involves a vulnerable population, namely pregnant women. All criteria as specified in "Special categories of research: Pregnant women, human fetuses, and neonates" delineated by the Mayo Clinic Office for Human Research Protection have been met to perform research involving pregnant women.

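### The primary analysis leaves preoperative hemoglobin out as a covariate although it is to be measured in everyone; adding it is a near-free gain in precision that may be nil, and the planned test is not wrong.

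*Combined protocol and SAP*

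**What the plan says.** Section 9.5 defines the primary analysis: a one-sided 95% confidence interval for the between-arm difference in mean drop, and in addition "the reduction in hemoglobin will be analyzed using a one-sided T-test using a change of .5g/dL". Neither names a covariate, and no other section plans a regression adjustment. Baseline enters only by subtraction, in forming the drop.

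Section 5.2 says that "preoperative hemoglobin and postoperative hemoglobin will be obtained for all study participants", and section 9.4.1 that "The preoperative hemoglobin will be performed on the day of surgery". Section 6 times the sample at admission for delivery. On either wording it precedes the sterilization procedure.

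Section 9.2 takes a margin of 0.5 g/dL, a common SD of 1.1 for the drop, one-sided alpha 0.05 and 60 women per arm for 80% power. The SD is set against a published "mean (SD) drop in hemoglobin of 1.32 (0.94) g/dl following a repeat cesarean delivery and 1.40 (1.2) following a first cesarean delivery", with over 75% repeat cesareans expected. The calculation is for a two-group t-test, so design and analysis agree. Section 9.3 states: "No interim analysis is planned".

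**The concern.** Subtracting the preoperative value fixes the slope of postoperative on preoperative hemoglobin at 1. If the true slope is below 1, part of the variation in the drop is predictable from the preoperative value, and the t-test leaves it in the error term. A linear model estimates the slope and removes that part.

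The loss is one of precision, not of validity. Randomization makes the unadjusted difference unbiased, and its standard error already allows for chance imbalance at baseline. Precision still matters in a non-inferiority trial: a wide interval can cross 0.5 g/dL, and the trial then fails to show non-inferiority, even when the procedures are equal. The design starts at about 80% power with no stated allowance for missing outcomes.

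Timing matters too. The plan prespecifies one unadjusted comparison, so an adjusted result can count as primary only if it is named before the arms are compared.

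**Working it through.** **Inputs from the documents** (sections 9.2 and 9.5): margin 0.5 g/dL; SD of the drop 1.1; one-sided alpha 0.05; 60 per arm; cited SDs 0.94 (repeat) and 1.2 (first), means 1.32 and 1.40; 75% repeat.

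**Assumed, because the documents do not give them:** preoperative SD 1.0 to 1.3, postoperative SD at least as large, slope not above 1, true difference 0, complete outcomes in 60 per arm.

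**1. The plan's own figure.** n per arm = 2 × 1.1² × (1.645 + 0.842)² / 0.5² ≈ 59.9, so 60. It reproduces. The exact noncentral-t power at 60 per arm (118 df) is 79.7%. The standard error is 1.1 × √(2/60) = 0.2008, and the distance from estimate to upper limit is 1.658 × 0.2008 = 0.333 g/dL.

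**2. Adjusted analysis, formulas.**
- Slope: b = (SDpre² + SDpost² − SDchange²) / (2 × SDpre²)
- Residual variance: SDchange² − (1 − b)² × SDpre²
- Standard error: residual SD × √[(2/60) × (1 + 1/116)], where 116 = 2 × 60 − 4 and the factor allows for estimating the slope; 117 df

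**3. Worked case, both SDs 1.0.** b = (1 + 1 − 1.21)/2 = 0.395. Residual variance = 1.21 − 0.605² = 0.844, so residual SD = 0.919. Standard error = 0.1685, distance to limit = 1.658 × 0.1685 = 0.279, power = 90.4%.

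**4. Range at SD of the drop 1.1.** The pre/post correlation is b × SDpre / SDpost.

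| SD pre | SD post | Slope | Pre/post correlation | Residual SD | Power |
|---|---|---|---|---|---|
| 1.0 | 1.0 | 0.395 | 0.40 | 0.919 | 90.4% |
| 1.1 | 1.1 | 0.500 | 0.50 | 0.953 | 88.5% |
| 1.2 | 1.2 | 0.580 | 0.58 | 0.978 | 87.0% |
| 1.3 | 1.3 | 0.642 | 0.64 | 0.997 | 85.9% |
| 1.0 | 1.2 | 0.615 | 0.51 | 1.030 | 83.8% |
| 1.0 | 1.3 | 0.740 | 0.57 | 1.069 | 81.4% |
| 1.0 | 1.4 | 0.875 | 0.63 | 1.093 | 79.8% |
| 1.0 | 1.49 | 1.000 | 0.67 | 1.100 | 79.4% |

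At slope 1 the distance to the limit is 0.334 g/dL, and adjustment costs 0.3 points of power. Because (1 − b) is squared, a slope above 1 would also give a gain, so capping it at 1 does not create the benefit.

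**5. At the cited SDs.** Overall SD = √(0.75 × 0.94² + 0.25 × 1.2² + 0.75 × 0.25 × 0.08²) = 1.012. The t-test then has 85.2% power. The adjusted analysis has 85.0% (slope 1) to 92.8% (both SDs 1.0), a change of −0.3 to +7.6 points.

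**6. Simulation check** (40,000 trials per setting). At SD 1.1, power for the t-test and the adjusted model was 79.7% and 90.4% with both SDs 1.0, and 79.7% and 79.4% at slope 1. At a true difference of 0.5, the rejection rate was 4.8% to 5.2% for the t-test and 4.8% to 5.1% for the adjusted model. Both hold their level.

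**7. Stratification factors.** Prior cesarean explains 0.75 × 0.25 × 0.08² / 1.012² = 0.12% of the variance on the cited means, so it adds almost nothing. The documents give no basis for judging BMI.

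**The case against.** The plan is internally consistent and its test is valid, so this is a choice between sound methods. The benefit rests on quantities that the documents do not report. The largest gain needs a pre/post correlation of only about 0.40, which is the favorable end of the range. With SDs of 1.0 and 1.4 the gain is 0.1 points. At the cited SDs the t-test already exceeds 80% power. All of that stands, and it is why this is an improvement and not a correction.

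A second objection concerns credibility. Section 9.3 rules out a formal interim analysis, but hemoglobin information still circulates during accrual. Section 7.3 grades adverse events partly by anemia, section 7.6 has charts reviewed after 10 patients and then at least quarterly, section 7.2 has operative reports reviewed after every 20, and section 8 counts graded events towards a hold. The surgical team knows the arm (section 6.2.2), and investigators enter the data (section 10.2). A change of primary analysis during the trial therefore has to be shown to be independent of accrued results. This stands as a condition on the fix. It is not a reason against it.

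Third, section 9.1 words the null loosely: it has salpingectomy's pre/post difference lower by at least 0.5 g/dL, which read as a drop points the other way. The upper limit used here follows the drop as defined in sections 9.2 and 9.5. The wording of 9.1 is a separate matter, but it is best tidied in the same amendment.

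**Conclusion.** The point holds as an improvement worth making, not as an error. The planned analysis is valid and matches its sample size, and 60 per arm need not change. Adding preoperative hemoglobin keeps the estimand, margin and alpha. At SD 1.1 it moves power from 79.7% to between 79.4% and 90.4%, and the distance to the limit from 0.333 to between 0.279 and 0.334 g/dL. The worst case costs one degree of freedom and about 0.3 points of power, and it needs a slope close to 1. Where in the range the trial falls cannot be settled from the documents, so confidence in the size of the gain is only moderate. The figures also assume that preoperative hemoglobin is in fact obtained for everyone, as planned. Adjustment loses no further patients, because the drop cannot be computed without that value.

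**What to change.** Amend section 9.5 before any outcome data are analyzed by arm:

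- Make the primary analysis a linear model for the hemoglobin drop with arm and preoperative hemoglobin.
- Compare the upper one-sided 95% limit of the adjusted difference (salpingectomy minus BTL) with 0.5 g/dL.
- Label the unadjusted t-test in advance as a sensitivity analysis.
- State that the choice rests on the design inputs and not on accrued data.

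The randomization strata may be added to match the design, but they must be settled first. The sample-size paragraph of the Précis says "The stratified block randomization will be according to number of prior cesarean deliveries (primary versus repeat cesarean delivery", without BMI. The design paragraph of the Précis and section 3 name both factors, as does section 9.2.1: "stratified according to number of prior cesarean deliveries (first versus repeat), and BMI (BMI < 35, BMI > 35". A BMI of exactly 35 falls in neither stratum and needs assigning.

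The cost is two or three sentences and an IRB submission, which section 12 already provides for: "This protocol and any amendments will be submitted to a properly constituted local Institutional Review Board". No new data and no new patients are needed.

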9 STATISTICAL CONSIDERATIONS

9.1 General Design Issues

The null hypothesis in this non-inferiority trial is that the mean difference in pre and postoperative hemoglobin of patients undergoing salpingectomy will be lower than that for patients undergoing BTL at the time of cesarean delivery by at least 0.5 g/dl. The alternative hypothesis to be proven is that this difference will be no lower than 0.5 g/dl.

A non-inferiority trial was chosen as the study aims to compare a less commonly performed procedure with a known and accepted standard. We want to show that the less common procedure is at as safe as the standard. Patients will be randomly assigned to salpingectomy or BTL at enrollment.

Primary hypothesis: The alternative hypothesis to be tested is that the mean difference in pre and postoperative hemoglobin of patients undergoing salpingectomy will be no lower than those that undergoing BTL at the time of cesarean delivery.

Primary variable: Mean hemoglobin change

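### The between-arm test planned for complications, readmission and reoperation cannot show how much excess risk the trial excludes; plan risk differences with 95% intervals

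*Combined protocol and SAP*

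**What the plan says.** Section 9.1 explains the choice of design: "We want to show that the less common procedure is at as safe as the standard". The hypotheses in that section are stated for the change in hemoglobin.

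Section 9.5 treats the endpoints differently. For the primary outcome, "A 1-sided 95% confidence interval will be constructed for the difference between study arms in the mean drop in hemoglobin", with a one-sided t-test against 0.5 g/dL. For everything else, "Secondary endpoints will be analyzed using two-sided T-test testing for a difference between the two study arms or a Chi-square test as appropriate". The decision rule is "Statistical significance will be determined using a p-value of 0.05". No interval, margin, expected rate or power is given for any binary safety endpoint.

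The list of those endpoints varies. The précis and section 3 name rates of complications, readmission and reoperation as secondary outcomes, and section 1.2 includes complications and readmission or return to the operating room. Section 9.4.2 lists complications but neither readmission nor reoperation. The last two therefore come under the rule in 9.5 only through the general term for secondary endpoints.

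**The concern.** A test for a difference asks whether the data contradict equal risk. The safety question is how much extra risk the data can rule out. With few events and 60 women per arm, the test will often be non-significant whether or not risk is raised, and a p-value alone does not reveal this. The protocol's own reasoning recognises the problem for hemoglobin, where it chose non-inferiority with a margin and an interval.

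The harms that sections 4.3 and 7.2 describe go beyond a fall in hemoglobin: transfusion, further surgery, and loss of the adnexa or uterus. Section 2.2 expects the results to inform counselling and perhaps to change practice. If the report sets non-significant complication and reoperation rates beside an aim of equal safety, readers may draw a conclusion that the data cannot carry.

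**Working it through.** **1. The plan's own figure.** Section 9.2 gives the margin ("Assuming that a difference of 0.5 in the drop in hemoglobin between study arms would be considered as equivalent"), the SD ("assuming a common standard deviation of 1.1") and the test ("This calculation is based on a two-group 0.05 1-sided t-test of equivalent in means"), with 80% power.

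n per arm = 2(1.645 + 0.842)² × 1.1² / 0.5² = 59.9, so 60. Power at 60 is 80.1% by the normal approximation and 79.7% by the noncentral t. The stated 60 per arm is reproduced, but it is sized for hemoglobin alone.

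**2. Power of the planned test for a doubling of risk.** Inputs: n = 60 per arm (9.2), all analysed; two-sided 0.05 (9.5). The control rate p₁ is an assumption shown as a range, because the documents give none; p₂ = 2p₁.

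Normal approximation, with p̄ the mean of the two rates:

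power = Φ{[(p₂ − p₁)√n − 1.96√(2p̄(1 − p̄))] / √(p₁(1 − p₁) + p₂(1 − p₂))}

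For 5% v 10%: (0.05 × 7.746 − 1.96 × 0.3725) / 0.3708 = −0.92, so power is 18%.

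The exact columns sum two Binomial(60) distributions over all tables in which the test is significant and salpingectomy has more events. The chi-square test is uncorrected.

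| BTL v salpingectomy | Approximate | Chi-square, exact | Fisher, exact |
|---|---|---|---|
| 1% v 2% | 6.5% | 1.8% | 0.1% |
| 2% v 4% | 9% | 7% | 1% |
| 5% v 10% | 18% | 17% | 9% |
| 10% v 20% | 33% | 33% | 25% |
| 15% v 30% | 50% | 51% | 42% |
| 20% v 40% | 67% | 68% | 60% |
| 25% v 50% | 82% | 82% | 76% |

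The chi-square test reaches even odds of detecting a doubling at a control rate of about 15%.

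**3. A check that needs no assumed rate.** Section 8 puts the study on hold at more than three Grade 3 events, so three is the largest number that does not trigger that rule. The most extreme split is 3 v 0. Chi-square = 120 × (3 × 60 − 57 × 0)² / (60 × 60 × 3 × 117) = 3.08, p = 0.079; Fisher p = 0.24. With no events in the other arm, significance needs at least 4 v 0 by chi-square (p = 0.042) or 6 v 0 by Fisher (p = 0.027).

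**4. What an interval adds.** Take 6/60 v 3/60. Chi-square = 120 × (6 × 57 − 54 × 3)² / (60 × 60 × 9 × 111) = 1.08, p = 0.30. The Wilson limits are 4.7% to 20.2% for 6/60 and 1.7% to 13.7% for 3/60. Newcombe's method combines them, in percentage points:

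- lower: 5.0 − √[(10.0 − 4.7)² + (13.7 − 5.0)²] = −5.2
- upper: 5.0 + √[(20.2 − 10.0)² + (5.0 − 1.7)²] = +15.7

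(The limits were computed before rounding.) The p-value reports no difference; the interval says that an excess of nearly 16 points is not excluded. Equal counts also leave room for excess risk. The upper limits are +6.0 points for 0 v 0, +7.3 for 1 v 1, +9.3 for 3 v 3 and +11.5 for 6 v 6.

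**The case against.** Four points can fairly be made for the plan.

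- **The formal claim is already narrow.** Section 2.2 frames the hypothesis as blood loss measured by hemoglobin drop, section 9.1 states its hypotheses on that scale, and the secondary objectives in 1.2 are worded as identifying rates. A reader might infer that the plan will treat non-significant secondary results as proof of equal safety. No section says so, and the risk is one of misreading. This stands, but the broad aim in 9.1 and the missing intervals leave the misreading open, and an aim of identifying rates calls for estimation.
- **Serious harm is also judged in other ways.** A reader might infer that these tests are the only check on safety. They are not. Section 7.3 classes return to the operating room as Grade 4, and section 8 puts the study on hold for any Grade 4 or 5 event, followed by a causality assessment; sections 7.2 and 7.6 add reviews of operative reports and charts. This also stands. These rules work on counts and case review, however, and make no comparison between arms.
- **The power figures rest on assumed rates.** Section 9.4.2 does not define complications, and section 7.3 counts mild anemia and increased pain as adverse events, so a broad composite could be common. At 20% v 40% the test has 68% power. The point is limited accordingly.
- **An interval does not add information.** It comes from the same counts, and the real limit is 60 women per arm. That is true. Its value is that it shows what has and has not been excluded.

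**Conclusion.** The concern holds for the between-arm analysis of binary safety endpoints. A test for a difference at 0.05, with no interval, does not address the aim in section 9.1. At 60 per arm and assumed control rates up to about 15%, a true doubling of risk would be non-significant about half the time or more: about 93% of the time at 2% v 4%, 83% at 5% v 10%, 67% at 10% v 20% and 49% at 15% v 30% by chi-square, and more often by Fisher. These figures assume complete data and rates that the documents do not supply.

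Two stronger readings are not supported. One is that the test misses a doubled risk whatever the rate; above about 15% it is more likely to detect it than not. The other is that the trial's main conclusion is undermined; the hemoglobin analysis has a margin, an interval and about 80% power, and is unaffected.

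**What to change.** In section 9.5, make the risk difference with a two-sided 95% Newcombe or score interval the main between-arm summary for binary safety endpoints. Name complications, readmission and reoperation there, and add the last two to 9.4.2 so that the lists agree. State that a non-significant test is not evidence of equal safety and that the non-inferiority conclusion covers the hemoglobin drop only.

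A formal non-inferiority test on these endpoints is not proposed. With an illustrative 5-point margin, one-sided 0.05, 80% power and equal true rates, n = 2(1.645 + 0.842)² p(1 − p) / 0.05² gives 97, 235 or 446 per arm at rates of 2%, 5% or 10%.

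The cost is a few lines of text and trivial analysis work, with no new data. The downside is that wide intervals will show openly how little excess risk the trial can exclude.
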